3.2 Outcome Measures

3.2.1 Primary and Secondary Immunogenicity Endpoints

Primary Immunogenicity Endpoints (Phase 2 and Phase 3): Immunogenicity Measures will Include:

- Percentage of subjects achieving an HAI titer $\geq 1:40$ after the second vaccination on Day 43.

[Note: this endpoint is equivalent to another commonly used endpoint of seroconversion as defined as prevaccination titer $< 1:10$ and a post-vaccination titer $\geq 1:40$ OR significant increase in antibody titer (a

pre-vaccination titer of $\geq 1:10$ and at least a four-fold increase in post-vaccination titer), since all subjects are expected to have baseline titer of $< 1:10$.]

Dose Selection Criteria for Phase 3: The higher vaccine dose tested (30 mcg) will be selected if it induces higher immune responses than the lower dose as described in the table below. Other factors such as safety and manufacturing costs will also be considered.

Dose	Percentage of subjects with HAI ≥ 40 after two vaccinations			
Low dose (15 mcg)	< 60%	60-64%	65-74%	$\geq 75\%$
High dose (30 mcg)	≥ 60	> 15 mcg dose	$> 13\%$ higher	Any
Dose selection	30 mcg	30 mcg	15 mcg, if $\Delta < 13\%$	15 mcg
			30 mcg if $\Delta \geq 13\%$	

Note Δ represent a difference in HAI in the high and low dose groups.

Success Criterion for Phase 3: the selected dose of vaccine induces responses in 60% or more of the approximately 300 subjects receiving the IVACFLU-A/H5N1 (vaccinees) selected for HAI immunogenicity testing.

Secondary Immunogenicity Endpoints: Immunogenicity Measures will Include:

Phase 2 (HAI and MN testing in all 300 Phase 2 subjects)

- Percentage of subjects with a serum HAI titer $\geq 1:40$ at Day 22.
- Percentage of subjects demonstrating an HAI seroresponse of at least a four-fold increase in post-vaccination titer on Day 22 and Day 43.
- Percentage of subjects with at least a four-fold rise in titer at Day 22 and Day 43, as determined by microneutralization (MN).
- Geometric Mean Titer (GMT) of Day 22 and Day 43 as determined by the HAI and MN tests.
- Geometric Mean Titer Ratio (GMTR) of Day 22/Day 1 and Day 43/Day 1 as determined by the HAI and MN tests.

Phase 3 [HAI testing in approximately 300 subjects receiving the IVACFLU-A/H5N1 (vaccinees); MN testing to be determined based on the results from Phase 2]

- Percentage of subjects demonstrating an HAI seroresponse of at least a four-fold increase in post-vaccination titer on Day 43.

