12.1 Study Hypothesis

The study hypothesis is that two 0.5 mL doses of whole virion monovalent A/H5N1 influenza vaccine (IVACFLU-A/H5N1) adjuvanted with alum will be safe and well tolerated in healthy adults, and that at least one of the two doses tested will be immunogenic in 60% or more of the subjects tested.

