12.3 Immunogenicity

The sample size calculations for the primary immunogenicity endpoints for Phase 3 are based on the following acceptance criteria:

- Percentage of subjects achieving HAI titer ≥ 40 on 21 days post-dose two should meet or exceed 60%.

For the Phase 2 dose selection component (Phase 2), samples from approximately 100 subjects per IVACFLU-A/H5N1 dose level will be tested by HAI and MNT assay. Phase 2 of this study is designed to provide 80% power to detect a 20 percentage points difference in response rates between the two dose groups (e.g. 50% for the 15 mcg dose vs. 70% for the 30 mcg dose). The minimum statistical difference that can be detected at two-sided 5% alpha is approximately 14 percentage points between the two dose groups (e.g. 50% for the 15 mcg dose vs. 64% for the 30 mcg dose). The selection of the dose for the Phase 3 will be based on multiple immunogenicity endpoints as listed in the primary and secondary immunogenicity endpoints. The power calculations were estimated based on the two-sided 0.05 Z test with unpooled variance using PASS 13.

For the Phase 3 component, samples from approximately 300 subjects receiving the IVACFLU-A/H5N1 (vaccinees) will be tested by HAI for the analysis of the immunogenicity endpoint. MN testing for the Phase 3 will be determined based on the results from Phase 2 and a determination that MN testing will add value to the Phase 3 study. The table below provides exact two-sided 95% CIs for either endpoints for different observed response rates for 300 evaluable subjects. This study is designed to provide the precision of the immune responses as estimated by the width of the confidence intervals less than ± 5.8 percentage points around the range of expected rates.

Observed Seroresponse Rate	Percentage of Subjects	Exact two-sided 95% CI
300/300	100%	[98.8%, 100%]
270/300	90.0%	[86.0%, 93.2%]
240/300	80.0%	[75.0%, 84.4%]
210/300	70.0%	[64.5%, 75.1%]

Observed Seroresponse Rate	Percentage of Subjects	Exact two-sided 95% CI
180/300	60.0%	[54.2%, 65.6%]
150/300	50.0%	[44.2%, 55.8%]

Also, this study with 300 evaluable subjects is designed to provide 97% and >99% probability to demonstrate adequate immune responses, $\geq 60\%$ achieving post-dose two HAI titer 1:40, if the true percentages of subjects achieving seroprotective level are 65% and 70%, respectively.

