Percentages of subjects with immune response will be calculated along the corresponding two-sided exact (Clopper-Pearson) binomial CIs. GMT and GMTR will be summarized by treatment group along with the corresponding two-sided 95% CIs, by exponentiating the corresponding log-transformed means and their 95% CIs. Titers below the lowest limit of quantitation (i.e., below the starting dilution of assay reported as “< 10”) will be set to half that limit (i.e., $10 / 2 = 5$). For Phase 2, two-sided 95% CIs for the difference in proportions of participants demonstrating seroresponse between the two dose groups will be based on the Newcombe hybrid score (METHOD=SCORE riskdiff-option for PROC FREQ in SAS). For the GMT and GMFR, two-sided 95% confidence intervals (95% CIs) for the ratios post-vaccination GMTs/GMFRs between two dose groups will be constructed using a log-normal distribution. The log values will be used to construct a 95% CI using t-distribution for the mean difference between the two treatment groups. Then the mean difference and the corresponding 95% CI limits will be exponentiated to obtain the GMT ratio and the corresponding CI. No comparisons will be made between the IVACFLU-A/H5N1 dose groups and the placebo group in both Phase 2 and Phase 3.

This study has a single primary endpoint and it maintains the experiment-wise Type I error rate at 2-sided of 0.05. No multiplicity adjustment to the error rate, alpha, will be made for secondary immunogenicity endpoints. Also no imputation of missing immunogenicity measures will be made.

13 Data Capture Methods

CRFs will be developed and data will be managed to the extent possible in accordance with internationally agreed-upon standards, such as the Clinical Data Acquisition Standards Harmonization, which defines basic standards for the collection of clinical trial data, and/or The Society for Clinical Data Management’s Good Clinical Data Management Guidelines.

All the information required by the study protocol must be recorded on the CRF provided by the sponsor, or if it is laboratory assay data, transferred in a format agreeable to the sponsor. All data must be entered legibly, as described in any *CRF Completion Guidelines*. An explanation must be provided for any missing data. Data entered onto the CRFs must be accurate, legible, contemporaneous, original (or traceable to the original source), and attributable.

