This IVACFLU-A/H5N1 Phase 2/3 is a double-blind, randomized, placebo-controlled trial to test the safety and immunogenicity of two doses given 21 days apart of the IVAC A/H5N1 vaccine. Subjects will be male and female healthy adults from 18 through 60 years of age. In the Phase 2 study which was a dose-selection study and was conducted at one site (Khanh Hoa), 300 male and female healthy adult subjects from 18 through 60 years of age were randomized to receive 15 mcg of vaccine (n=100), 30 mcg of vaccine (n=100), or saline placebo (n=100). The details of the interim analysis plan for the Phase 2 study had been prepared separately.

The Phase 3 is a confirmatory study that will expand the safety and immunogenicity in a larger number of subjects to meet product registration in Vietnam. In Phase 3, subjects will be randomized to receive the selected vaccine 15 mcg dose (n=500) or saline placebo (n=100) under double blind. Safety will be assessed in all subjects and immunogenicity will be measured by Hemagglutination Inhibition test (HAI) in a subset of approximately 270 subjects receiving the IVACFLU-A/H5N1 (n=225 vaccinees) and placebo (N=45) from all subjects enrolled at one of 2 study sites (Hai Phong) in Phase 3.

This final analysis plan will mainly focus on the analyses of Phase 3 cohort with additional analyses combining subjects from both phases if needed.

I. OBJECTIVES

The study objectives and endpoints for Phase 3 as described in the protocol are as follows:

Primary Objective	Endpoint

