Before unblinding the study data, FHI360 statisticians will provide blinded data to the study statistician and the study medical officer to establish the criteria for exclusion of subjects from the Full Analysis Population and Per Protocol Population, and to review protocol violations. The final data analysis will initially be prepared with blinded study product group. After all analysis programs and output tables for the final analyses are verified, all analysis programs will be re-ran with the unblinded study product code given by the study randomisation statistician. In addition, the FHI360 randomisation statistician will verify with IVAC that no errors were made in study product assignment and dispensing of vaccines.

V. MULTIPLICITY CONSIDERATION

In general, since the purpose of the Phase 2 assessment is to select the dose for the Phase 3 component and the final confirmatory analysis will be solely based on the data generated for the Phase 3 component, there is no need to make an adjustment to the Type I error rate between the Phase 2 and Phase 3 components of the study.

Specifically, the analysis of immunogenicity data has a single primary endpoint and it maintains the experiment-wise Type I error rate at 2-sided of 0.05. No multiplicity adjustment to the error rate, alpha, will be made for secondary immunogenicity endpoints.

In addition, no formal hypothesis testing will be conducted for safety data analyses, therefore, no multiplicity adjustment will be performed.

VI. DESCRIPTIVE ANALYSIS

A. Study Participant Disposition

A flowchart or table showing the number screened, enrolled, randomized, vaccinated, withdrawn and its reasons, and numbers in the Full Analysis and Per Protocol Populations with protocol deviations reported on the Protocol Deviation/Violation (PDV) CRF will be produced.

B. Descriptive Statistics

Descriptive statistics will be presented in summary tables by each group, each time visit and overall. Categorical variables will be summarized by frequencies and percentages. Continuous variables will be summarized by means, standard deviations, medians, interquartile ranges, minima and maxima.

C. Baseline Data

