Analysis Population: All immunogenicity endpoint analyses and summaries will be performed on a per-protocol basis for all subjects and by age group (18-40 years of age and 41-60 years age). Supportive analysis will also be conducted on participants in the FA population who received at least one dose of study vaccines if the difference in the number of subjects between the FA and PP populations exceeds 5%.

Study Endpoints

Primary:

- Percentage of subjects achieving an HAI titer $\geq 1:40$ after the second vaccination on Day 43

Secondary:

- The percentage of subjects achieving a seroresponse (at least a four-fold increase in post-vaccination titer) on Day 43 as determined by HAI
- Geometric Mean Titer (GMT) of Day 43 as determined by HAI.

³ Horne AD, Lachenbruch PA, Getson PR, and Hsu HS Analysis of Studies to Evaluate Immune Response to Combination Vaccines. Clinical Infectious Diseases 2001; 33(Suppl 4):S306-11

- Geometric Mean Titer Ratio (GMTR) of Day 43/Day 1 as determined by HAI.

Analysis Methods

There are two types of immunogenicity measurements, percentages of subjects with immune response and Geometric Mean Titers (GMT), that will be used to evaluate this study objective.

Percentages of subjects with immune response:

- Percentage of subjects achieving an HAI titer $\geq 1:40$ ⁴ on Day 43.
- Percentage of subjects demonstrating an HAI seroresponse of at least a four-fold increase in postvaccination titer on Day 43.

For each percentage of subjects with the defined immune responses, the percentage and its corresponding 2-sided exact (Clopper-Pearson) binomial 95% confidence interval (95% CI) around the percentage will be computed for each treatment group and by age group.

Geometric Mean Titers (GMTs):

- Geometric Mean Titer (GMT) of Day 43 as determined by HAI
- Geometric Mean Fold Rise (GMFR): Geometric Mean of Titer Ratio of Day 43/Day 1 as determined by HAI.

GMT along with the corresponding two-sided 95% CIs, by exponentiating the corresponding log-transformed means and their 95% CIs, will be summarized by treatment group on Day 1 and Day 43. The same approach will be used to summarize GMFR of Day 43/Day 1 separately by treatment group and age group.

Furthermore, the analyses will be repeated by combining the immunogenicity measures of the selected dose group and the placebo group from both Phases 2 and 3 cohorts if needed. No comparisons will be made between the IVACFLU-A/H5N1 dose group and the placebo group.

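### The plan claims a two-sided 0.05 Type I error for a Phase 3 primary endpoint that is judged on the observed rate alone; a vaccine just below 60% passes about 52% of the time

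*Protocol*

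**What the plan says.** - **Error claim.** Protocol 12.4.3: "This study has a single primary endpoint and it maintains the experiment-wise Type I error rate at 2-sided of 0.05". Final SAP V (Multiplicity Consideration): "the analysis of immunogenicity data has a single primary endpoint and it maintains the experiment-wise Type I error rate at 2-sided of 0.05". In the SAP this comes directly after the statement that the confirmatory analysis rests on Phase 3 data only.
- **Hypothesis.** Protocol 12.1: "at least one of the two doses tested will be immunogenic in 60% or more of the subjects tested".
- **Success rule.** Protocol 3.2.1: "Success Criterion for Phase 3: the selected dose of vaccine induces responses in 60% or more of the approximately 300 subjects". The acceptance criterion used for sizing in Protocol 12.3 is the same: the percentage with HAI of at least 40 "on 21 days post-dose two should meet or exceed 60" percent.
- **Stated success probability.** Protocol 12.3: "this study with 300 evaluable subjects is designed to provide 97% and >99% probability to demonstrate adequate immune responses", for true rates of 65% and 70%.
- **Planned analysis.** Protocol 12.4.3 and final SAP VII give a percentage with an exact (Clopper-Pearson) 95% CI per group. Final SAP VII adds: "No comparisons will be made between the IVACFLU-A/H5N1 dose group and the placebo group". It does not contain the 60% criterion.
- **Number tested.** Protocol 12.3 assumes 300 evaluable vaccinees. The final SAP Preface has "approximately 270 subjects receiving the IVACFLU-A/H5N1 (n=225 vaccinees) and placebo (N=45").

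**The concern.** A Type I error rate belongs to a test of a stated null hypothesis. For the Phase 3 primary endpoint the documents give no null value, no test, and no rule linking the confidence interval to 60%. The 0.05 therefore describes nothing that will be done in Phase 3. Both documents call Phase 3 the confirmatory study for registration. A reader of Protocol 12.4.3 or final SAP V would credit a pass with an error control that the design does not provide. The claim in Protocol 12.3 that the study can demonstrate adequate responses adds to that impression.

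**Working it through.** **Inputs.** Threshold 60% (Protocol 3.2.1, 12.1, 12.3). n = 300 vaccinees (Protocol 12.3) or 225 (final SAP Preface). True rates 65% and 70% (Protocol 12.3). X is the number of vaccinees with HAI of at least 1:40 at Day 43, taken as Binomial(n, p).

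**Step 1. Which rule produced the protocol's figures?** An observed rate of at least 60% with n = 300 means X ≥ 0.60 × 300 = 180.

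| Rule, n = 300 | p = 65% | p = 70% |
|---|---|---|
| Stated in Protocol 12.3 | 97% | >99% |
| Observed rate ≥ 60%: P(X ≥ 180) | 96.9% | 99.99% |
| Exact 95% lower limit ≥ 60%: P(X ≥ 198) | 38.3% | 94.1% |

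The stated figures come from the observed-rate rule and cannot come from a lower-limit rule.

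**Step 2. How often does a vaccine below 60% pass?** The hypothesis is a rate of 60% or more, so a false pass is a pass at a true rate below 60%. For n = 225 the rule is X ≥ 0.60 × 225 = 135.

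| True rate | n = 300, P(X ≥ 180) | n = 225, P(X ≥ 135) |
|---|---|---|
| 59.99% | 52.4% | 52.8% |
| 59.9% | 51.1% | 51.7% |
| 59% | 38.6% | 40.8% |
| 58% | 26.1% | 29.5% |
| 55% | 4.6% | 7.4% |

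Type I error is the worst case over the null, so the figure to set against 0.05 (0.025 in the direction of success) is about 0.52.

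**Step 3. What does a bare pass show?** The exact 95% CI is 54.2% to 65.6% for 180/300, which is also the row printed in Protocol 12.3. For 135/225 it is 53.3% to 66.5%.

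**Step 4. The favourable side at n = 225.** Under the same rule the pass probability is 94.9% at a true 65%, not 97%, and 99.9% at 70%.

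**Step 5. What would a rule with error control need?** Success would be an exact two-sided 95% lower limit of at least 60%.

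| | n = 300 | n = 225 |
|---|---|---|
| Responders needed | 198 (66.0%) | 150 (66.7%) |
| Lower limit there; one responder fewer | 60.33%; 59.99% | 60.10%; 59.64% |
| Pass probability at p = 60% | 1.9% | 2.3% |
| Power at 65% | 38.3% | 32.7% |
| Power at 70% | 94.1% | 87.7% |

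**Step 6. Could the 0.05 refer to another Phase 3 analysis?** There is one dose, so there is no dose comparison. The comparison with placebo is excluded. Final SAP V says no formal hypothesis testing is done for safety. No candidate remains.

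**The case against.** **The sentence may refer to Phase 2.** Protocol 12.4.3 speaks of the whole study, and Protocol 12.3 does describe a two-sided 0.05 comparison of the two doses on the same endpoint. This stands as a possible reading of the protocol, which is why limiting the claim to Phase 2 is one of the remedies. It is also why the Phase 2 interim SAP is not criticised here. It cannot rescue final SAP V, whose main subject is the Phase 3 cohort with a single dose.

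**The sentence is only about multiplicity.** The heading in the SAP supports this. But having one endpoint only prevents inflation of a 0.05-level test, and here there is no such test.

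**The observed-rate rule is stated openly and may suit the regulator.** That is true. Protocol 12.3 prints the wide interval for 180/300 and also describes Phase 3 in terms of CI precision. Nothing here says the rule is unacceptable, only that it does not carry the claimed error rate.

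**The 52% is a boundary figure, and Phase 2 is a prior gate.** Both are fair. The gate requires at least 60% in at least one dose group of 100. Assume independent groups and phases. At a true 59.99% one group of 100 passes with probability 0.5425.
- If only one dose can pass: 0.5425 × 0.5236 = 0.28.
- If both doses have that rate: (1 − 0.4575²) × 0.5236 = 0.41.

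At a true 58% the same products are 0.3826 × 0.2606 = 0.10 and (1 − 0.6174²) × 0.2606 = 0.16. All exceed 0.05, and the plan rests confirmation on Phase 3 alone.

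**The documents are from different stages.** The final SAP describes a smaller Phase 3 (500 vaccine and 100 placebo subjects at 2 sites) than the protocol (1,000 and 500 at 3 sites). So the n = 225 figures assume that the 60% rule carries over. The conclusion is the same at either number.

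**Conclusion.** The concern holds. As written, Protocol 12.4.3 (for Phase 3) and final SAP V attribute to the confirmatory primary endpoint a two-sided 0.05 Type I error that the design does not have. Under the only success rule stated, the chance of passing just below 60% is about 52% with 300 or 225 vaccinees, falling to 26–30% at a true 58% and 5–7% at 55%. This rests on exact binomial calculation, on taking a true rate below 60% as the null (the documents state none, and 60% is the only threshold they give), and on the 60% rule applying at n = 225. The planned estimates and intervals are sound; the error is in the property claimed for them. Because it concerns the primary endpoint of the registration study, it must be corrected.

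**What to change.** **Main option, keeping the sponsor's rule.**
- In Protocol 12.4.3 and final SAP V, delete the 0.05 claim for the Phase 3 primary endpoint, or restrict it in the protocol to the Phase 2 dose comparison. State that Phase 3 success is an observed-rate criterion without Type I error control against 60%.
- Put the 60% criterion into final SAP VII, and word a pass as an observed rate of at least 60%, reported with the exact 95% CI already planned.
- In Protocol 12.3, set the pass probabilities at true rates of 55%, 58% and just below 60% beside the favourable ones, for the number of vaccinees actually tested.

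This costs wording only: no subjects, samples or new analyses. The stated properties become less favourable.

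**If a 0.05-level claim is wanted.** Define success as an exact two-sided 95% lower limit of at least 60% (198/300 or 150/225). Restate power at true rates of 65%/70% as 38%/94% for n = 300 or 33%/88% for n = 225. The price is the low power at 65%. Accepting that power needs no added subjects; raising it would need more vaccinees tested.

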13.1 Database Management and Analysis Software

A detailed statistical analysis plan for preparation of the final study report will be created and made final prior to database lock and unblinding. All statistical analyses will be performed using SAS® software Version 9.2 or later.

Medical history and AEs will be coded using MedDRA dictionary Version 15.1. The frequency count and percentage of subjects will be summarized according to the coded terms of system organ class and preferred term. Subject-wise data listings will be provided.

13.2 Entering, Cleaning, and Management of the Database

Procedure of entering, cleansing, and management of the database will be developed and implemented by Contract Research Organization (CRO). CRO will perform data management, data analysis, and report writing. A Data Management Plan will be drafted by CRO and submitted to IVAC, PATH, and WHO to approval before implementation.

13.3 Potential Deviations and Method of Limiting Deviations

To limit the potential deviations, the trial uses the double blinded, randomized, and placebo-controlled study design.

To further limit the potential deviations, during the study process, the most critical study activities will be based on standard operation procedures (SOPs), particularly the activities related to the study record database, copying data from source documents, data entry, and the cleaning process. During the data entry process, the questionable, inappropriate data will be detected by the data management system developed by the CRO with data management responsibilities, and feedback will be given to clarify the questionable data via a data clarification form / DCF. All fixes on CRF must be signed by study staff and the fix date must be recorded.

14 Source Documents and Source Document Access

Prior to the start of the trial, the sponsor will determine which documents or data fields completed by the investigative team will be considered source documents and documented on a Source Documentation Table. Source documents for this study may be outpatient charts, inpatient charts, laboratory analysis forms, Diary Cards, and specimen collection logs. For some data fields, the CRF may be the source document. Data fields on the CRF for which there are separate primary source documents will be carefully completed using the named source document.

Only authorized study staff and representatives of IVAC and study monitors authorized by IVAC, PATH, overseeing ethical review committees, and regulatory agencies may have direct access to source documents containing study data. Subject identification will be revealed to authorized representatives of these organizations only when necessary.

15 Quality Control and Quality Assurance

